APPENDICES.....	55
APPENDIX A: PARTICIPANT ELIGIBILITY CHECKLIST	55

PROTOCOL SYNOPSIS

TITLE	Abemaciclib in metastatic or locally advanced Anaplastic/Undifferentiated Thyroid Cancer
STUDY PHASE	Phase 2
INDICATION	Anaplastic/Undifferentiated Thyroid Cancer without curative option
INVESTIGATIONAL PRODUCT OR PROCEDURE	Abemaciclib
PRIMARY OBJECTIVE(S)	Overall response rate
SECONDARY OBJECTIVE(S)	Overall Survival

	Progression Free Survival Safety Analysis
TREATMENT SUMMARY	Until progression/intolerance of therapy. Projected 2 to 6 months per patient
SAMPLE SIZE	Simon's Stage 1 (n=9): at least 1 response required to continue to Stage 2 Simon's Stage 2 (additional 8 patients, total n=17)
STATISTICAL CONSIDERATIONS	Simon's optimal two-stage design (Simon, 1989) will be used.

SCHEMA

Pre-Screening portion: molecular analysis will be performed to determine if patients have *BRAF V600E* negative ATC/UTC. These will be treated with Abemaciclib

Therapeutic portion:

[figure not shown]

Fig 1-1 Trial schema

LIST OF ABBREVIATIONS AND DEFINITION OF TERMS

AE	Adverse Event
ALCL	Anaplastic large cell lymphomas
ALK	Anaplastic lymphoma kinase
ALT	Alanine aminotransferase/glutamic pyruvic transaminase/GPT
AST	Aspartate aminotransferase/glutamic oxaloacetic transaminase/GOT
ATC	Anaplastic Thyroid Cancer
BCRP	multidrug transporter ABCG2
b.i.d.	bis in diem/twice a day
CNS	Central nervous system
CR	Complete Response
CrCl	creatinine clearance
CRO	Contract Research Organization
DLT	Dose Limiting Toxicity
DS&E	Drug Safety and Epidemiology
ECG	Electrocardiogram
EIAED	enzyme inducing anti-epileptic medication
EGFR	epidermal growth factor receptor
EOT	End of treatment
FAS	Full Analysis Set
GI	Gastric intestinal
hERG	human Ether-à-go-go-Related Gene
IUD	intrauterine device
IUS	intrauterine system
i.v.	intravenous (iv)
ICH	International Conference on Harmonization
IEC	Independent Ethics Committee
IHC	immunohistochemistry
IRB	Institutional Review Board
LLN	Lower limit of normal
LLNA	local lymph node assay
MTD	Maximum Tolerated Dose NSCLC non-small cell lung cancer
o.d.	omnia die/once a day

OS	Overall survival
OTC	over-the counter
QD	once daily
PD	Progressive disease
p.o.	per os/by mouth/orally
PFS	Progression free survival
PHI	Protected Health Information
PK	Pharmacokinetics
PPI	proton pump inhibitors
PR	Partial response
Racc	accumulation ratio
RAP	The Report and Analysis Plan (RAP) is a regulatory document which provides evidence of preplanned analyses
RDE	Recommended dose for expansion
REB	Research Ethics Board
RECIST	Response Evaluation Criteria In Solid Tumors
RR	Response Rate
SAE	Serious Adverse Event
SOP	Standard Operating Procedure
TDI	time-dependent inhibition
TKI	tyrosine kinase inhibitors
ULN	upper limit of normal
UTC	Undifferentiated thyroid cancer
UV	Ultraviolet radiation
VATS	Video-assisted thoracic surgery
VEGF	vascular endothelial growth factor
WHO	World Health Organization

1. OBJECTIVES

1.1. Primary Objective

The primary objective is to determine the overall response rate after treatment with abemaciclib in patients with anaplastic thyroid/undifferentiated thyroid cancer.

1.2. Secondary Objectives

The secondary objectives are to describe the overall survival (OS) and progression-free survival (PFS) after treatment with abemaciclib in patients with anaplastic thyroid/undifferentiated thyroid cancer. Safety assessments of AE's will also be analysed.

2. BACKGROUND

2.1 Study Disease

2.1.1 Anaplastic Thyroid Cancer

Anaplastic thyroid cancer (ATC) is an undifferentiated tumor of thyroidal follicular epithelium. Although not as common as differentiated thyroid cancers, ATC has much higher disease specific mortality, approaching 100% (Are and Shaha 2006).). In fact, despite accounting for less than 5% of all thyroid cancer diagnoses, ATC leads to more than half of the 1200 deaths from thyroid cancer every year in the United States (Hundahl, Fleming et al. 1998, McIver, Hay et al. 2001).

Forty six percent of patients present with distant metastases, and almost 70% demonstrate metastases at some stage of the disease (McIver, Hay et al. 2001). All staging for anaplastic thyroid cancer is as stage IV (McIver, Hay et al. 2001), given its aggressive nature and propensity for metastasis. Even with the most aggressive existing multimodality therapy involving surgery, radiation and chemotherapy, most patients do not derive consistent, sustained benefit in outcomes and survival. Median overall survival remains 3-4 months, with 90% of patients dead at 1 year from diagnosis (McIver, Hay et al. 2001). Patients often suffer from distant metastases even after local therapy is completed, demonstrating the inadequacy of treatment. Lung, brain and bone metastases are common as well as significant airway compromise and suffocation even after tracheostomy.

2.1.2 Treatment for Anaplastic Thyroid Cancer-Chemotherapy

Doxorubicin is the only approved chemotherapy for anaplastic thyroid cancer (Smallridge, Ain et al. 2012), and is often combined with radiation or surgery as part of multi-modality therapy. No randomized trial has demonstrated improved statistically significant survival or better quality of life in patients treated with any current therapy (Smallridge, Ain et al. 2012).

Given the poor prognosis, guidelines from the American Thyroid Association as well as the National Comprehensive Cancer Network recommend all patients should be treated as part of a clinical trial regardless of stage (NCCN clinical practice guidelines in Oncology , Smallridge, Ain et al. 2012).

This treatment protocol aims to offer targeted, mutation and oncogene driven therapy for patients with anaplastic thyroid cancer who would otherwise have very poor treatment options and outcome.

As new biomarkers and drug combinations are identified, additional arms will be added to the therapeutic portion of the study based on that knowledge.

2.1.3 Treatment for Anaplastic Thyroid Cancer-Targeted Therapy and Clinical Trials

There are currently no approved and no commonly employed targeted therapies in anaplastic thyroid cancer. This is an area of urgent need for patients, not just for approved treatments but also rationally-designed clinical trials designed specifically for ATC.

Newer agents have been tested in patients with ATC, but currently none have been approved for any stage of therapy for patients in the US. Fosbretabulin is a novel tubulin binding compound that demonstrated activity in ATC (Mooney, Nagaiah et al. 2009). A Phase III trial randomized ATC patients to fosbretabulin or placebo, these patients had previously been treated with carboplatin and paclitaxel and 55% of them had undergone surgical resection (Sosa, Balkissoon et al. 2012). The arm containing the experimental drug had 33.3% survival at one year vs 7% for the carboplatin and paclitaxel alone arm. Although not powered to detect differences in survival, the median survival for the standard arm was reported as 4 months for the control arm versus 8.4 months for the fosbretabulin arm.

Sorafenib has demonstrated some activity in multi-institution, small studies. In 20 patients treated with sorafenib, 2 patients demonstrated a partial response (Savvides, Nagaiah et al. 2013). Sorafenib is currently not listed as a recommended regimen in the NCCN guidelines for anaplastic thyroid cancer, nor in the ATA guidelines for Anaplastic Thyroid Cancer.

A minority of ATC patients have a BRAF V600E mutation are offered dabrafenib and trametinib as treatment. These drugs are not curative, and they then require further therapy. These patients often need to start subsequent therapy quickly because they have rapidly growing tumors.

Patients whose most recent treatment has been with only dabrafenib and trametinib may be enrolled on to the study and start abemaciclib 1 week after discontinuation of dabrafenib and trametinib, instead of 3 weeks as is required for cytotoxic chemotherapies. Dabrafenib and trametinib have short half lives and upon discontinuation there is rapid clearance of these drugs and resolution of their toxicities.

Additionally some patients are treated with lenvatinib, though the FDA label limits the indication to differentiated thyroid cancer. Lenvatinib has a half-life of 28 hours per the package insert.

https://www.accessdata.fda.gov/drugsatfda_docs/label/2018/206947s007lbl.pdf. Due to this short half life a washout period of 1 week is sufficient to reach a point where there is minimal lenvatinib.

Clinical trials for this disease are also extremely rare, leaving patients with very limited treatment options. Patients diagnosed with anaplastic thyroid cancer have a very high likelihood of dying because of their disease. As such there is a clear need for improving therapy for anaplastic thyroid cancer in a rational, patient selective manner.

2.2 Study Agent/Device/Procedure

In the mammalian cell cycle, entry into S phase is achieved by CDK4/6. Abemaciclib is a small molecule inhibitor that is selective for CDK4 and 6. It blocks phosphorylation of the retinoblastoma tumor suppressor protein. This leads to impaired progression through the cell cycle and arrest in the G1 phase(Sledge, Toi et al. 2017). Currently, Abemaciclib is FDA-approved for use in breast cancer, with the package insert providing further information about pharmacology, dosage and administration, drug interactions and use in special populations:

https://www.accessdata.fda.gov/drugsatfda_docs/label/2017/208716s000lbl.pdf

For clinicaltrials.gov compliance

Abemaciclib is FDA approved for use in breast cancer. This clinical trial will not be seeking a new indication. An IND is not required in conjunction with this clinical trial.

2.3 Rationale

Experimental Therapy: Abemaciclib

2.3.1 Evidence suggesting benefit of abemaciclib in ATC/UTC

Retinoblastoma,CDNK2A/p16 in ATC/UTC

Retinoblastoma (Rb) is a critical negative regulator of the cell cycle which prevents premature cell division(Schwartz and Shah 2005). Rb inactivation leads to uncontrolled cell division, and has been detected in many cancers, for example breast (20-30%)(Bosco and Knudsen 2007). In tumors with functional Rb, CDK 4/6 inhibitors inhibit cell growth and suppress DNA replication(Fry, Harvey et al. 2004). In Rb-deficient tumors, CDK 4/6 inhibitors have limited efficacy(Dean, Thangavel et al. 2010). Rb mutations have been reported in thyroid

cancer cases, but there is a dichotomy based on histologic sub-type, as differentiated thyroid cancers often lose Rb but more aggressive variants such as ATC almost always have intact Rb (Anwar, Emond et al. 2000).

In an analysis of Rb staining in thyroid cancers, 4 anaplastic thyroid cancer samples all showed strong positive Rb expression (Anwar, Emond et al. 2000). By contrast, all of the more common papillary thyroid cancers and follicular variant of papillary showed entirely negative staining for Rb (table). Other subtypes showed a varied staining pattern, such as medullary thyroid cancer (50% Rb positive) and Hurthle cell (20% Rb positive). This shows that anaplastic is unique amongst thyroid cancers in expressing intact Rb, suggesting a role for CDK 4/6 inhibition.

The p16 mutation inhibits CDK4/6 which phosphorylates Rb, resulting in cell cycle progression. High p16 levels are seen in some cancers, such as human papilloma virus (HPV) associated head and neck squamous cell cancer. The true value of p16 as a predictive biomarker for CDK4/6 inhibition is still being analyzed. However current thinking suggests that if p16 levels are high, it is likely that pharmacological inhibition of CDK4/6 would be less effective.

In anaplastic thyroid cancer p16 levels were undetectable in 24 out of 27 (89%) cancer specimens (Lee, Foukakis et al. 2007).

CDKN2A encodes the cell cycle regulator p16. There was deletion or LOH in 3/5 anaplastic thyroid cancer specimens (Tung, Shevlin et al. 1996). Using 90 ATC patient samples, we performed comprehensive genomic profiling to determine the frequency of CDKN2A loss. These data were presented at ASCO 2016 and published results (Khan, Ci et al. 2019) showed more than 30% of ATC patients demonstrate loss of CDKN2A. Rb1 loss was seen in 2/90 patients.

2.4 Study Design

This study will be an open-label, single cohort study for the purpose of evaluating the efficacy of treatment with abemaciclib in patients with analplastic thyroid/undifferentiated thyroid cancer. There will be no randomization. An optimal Simon 2 stage design will be utilized to address the primary objective.

2.5 Correlative Studies Background

See above; no correlative studies will be done in this study.

3. PARTICIPANT SELECTION AND ENROLLMENT PROCEDURES

Patient population

Subjects from this study will be selected from those with anaplastic or undifferentiated thyroid cancer. Patients with a histologically confirmed diagnosis of anaplastic or undifferentiated thyroid cancer will be eligible to be enrolled on to the pre-screening portion of the trial. Molecular testing is considered standard for these patients using next generation sequencing platforms that have broad coverage of many genes.

Patients enrolled to the therapeutic portion of the study will have histologically proven anaplastic or undifferentiated anaplastic thyroid cancer that is BRAF V600E negative.

Patients that have a documented BRAF V600E positive ATC/UTC will be treated first with BRAF targeted therapy, currently the FDA approved regimen is combination of dabrafenib and trametinib. Patients will be eligible for abemaciclib therapy after they have progressed on this combination or become intolerant.

3.1 Inclusion Criteria

Patients eligible for inclusion in this early treatment protocol have to meet **all** of the following criteria:

1. Histologically or cytologically confirmed diagnosis of anaplastic thyroid cancer or undifferentiated thyroid cancer that does not have a known BRAF V600E positive on tissue/blood testing. BRAF V600E positive patients are eligible if they have previously received FDA approved therapy for this genetic abnormality and progressed or become intolerant.
2. Patients will be eligible if they meet either criteria:
 - a. Unresectable anaplastic thyroid cancer limited to the neck: Patients must have received radiation therapy or surgery to primary tumor and have subsequent evidence of ATC.
 - b. Metastatic anaplastic thyroid cancer: either with entirely surgically removed cancer/metastatic only disease, or with disease in the neck not requiring radiation or surgery to the neck mass.
3. Patients with a bulky thyroid/neck mass and those in whom airway obstruction is suspected should undergo an evaluation via indirect or direct laryngoscopy to ensure patency of the trachea/airway prior to enrollment
4. Patients will not have any other curative therapeutic option, such as radiation or surgery.
5. ECOG performance status 0-1.

6. Have measurable disease based on RECIST 1.1
7. Be willing to provide tissue from a newly obtained core or excisional biopsy of a tumor lesion. Newly-obtained is defined as a specimen obtained up to 6 weeks (42 days) prior to initiation of treatment on Day 1. Subjects for whom newly-obtained samples cannot be provided (e.g. inaccessible or subject safety concern) may submit an archived sample.
8. Be ≥ 18 years of age on day of signing informed consent.
9. Patients who received chemotherapy must have recovered (Common Terminology Criteria for Adverse Events [CTCAE] Grade ≤ 1) from the acute effects of chemotherapy except for residual alopecia or Grade 2 peripheral neuropathy prior to study treatment start. A washout period of at least 21 days is required between last chemotherapy dose and study treatment start (provided the patient did not receive radiotherapy). Note: Patients who have most recently been treated with dabrafenib and/or trametinib and/or lenvatinib require a washout period of 1 week from their last dose
10. Patients who received radiotherapy must have completed and fully recovered from the acute effects of radiotherapy. A washout period of at least 14 days is required between end of radiotherapy and study treatment start.
11. The patient is able to swallow oral medications.
12. The patient has adequate organ function for all of the following criteria, as defined in Table 3-1 below:

Table 3-1: Laboratory Value Guidance to Establish Adequate Organ Function

System	Laboratory Value
Hematologic	
ANC	$\geq 1.5 \times 10^9/L$
Platelets	$\geq 100 \times 10^9/L$
Hemoglobin	$\geq 8 \text{ g/dL}$
	Patients may receive erythrocyte transfusions to achieve this hemoglobin level at the discretion of the investigator. Initial treatment must not begin earlier than the day after the erythrocyte transfusion.
Hepatic	
Total bilirubin	$\leq 1.5 \times \text{ULN}$ Patients with Gilbert's syndrome with a total bilirubin ≤ 2.0 times ULN and direct bilirubin within normal limits are permitted.
ALT and AST	$\leq 3 \times \text{ULN}$

Abbreviations: ALT = alanine aminotransferase; ANC = absolute neutrophil count; AST = aspartate aminotransferase; ULN = upper limit of normal.

13. Women of childbearing potential and all men must agree to use adequate contraception (hormonal or barrier method of birth control; abstinence) while taking drug and agree to continue for 3 months after the last dose of study treatment. Women of child bearing potential and male patients for 3 months should not mother or father a child in this period. A condom is required to be used also by vasectomized men in order to prevent delivery of the drug via seminal fluid.
14. Patient has the ability to understand and provide signed informed consent.
15. Willingness and ability to comply with scheduled visits, treatment plans, laboratory tests and other procedures.

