8. CORRELATIVE/SPECIAL STUDIES

No study specific correlative procedures are planned. Analysis of exploratory biomarkers will utilize data derived from standard of care testing platforms.

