3. Patients with a bulky thyroid/neck mass and those in whom airway obstruction is suspected should undergo an evaluation via indirect or direct laryngoscopy to ensure patency of the trachea/airway prior to enrollment			
4. Patients will not have any other curative therapeutic option, such as radiation or surgery.			
5. ECOG performance status 0-1.			
6. Have measurable disease based on RECIST 1.1.			
7. Be willing to provide tissue from a newly obtained core or excisional biopsy of a tumor lesion. Newly-obtained is defined as a specimen obtained up to 6 weeks (42 days) prior to initiation of treatment on Day 1. Subjects for whom newly-obtained samples cannot be provided (e.g. inaccessible or subject safety concern) may submit an archived sample.			

8. Be \geq 18 years of age on day of signing informed consent.			
9. Patients who received chemotherapy must have recovered (Common Terminology Criteria for Adverse Events [CTCAE] Grade \leq 1) from the acute effects of chemotherapy except for residual alopecia or Grade 2 peripheral neuropathy prior to study treatment start. A washout period of at least 21 days is required between last chemotherapy dose and study treatment start (provided the patient did not receive radiotherapy). Note: Patients who have most recently been treated with dabrafenib and/or trametinib and/or lenvatinib require a washout period of 1 week from their last dose			
10. Patients who received radiotherapy must have completed and fully recovered from the acute effects of radiotherapy. A washout period of at least 14 days is required between end of radiotherapy and study treatment start.			
11. The patient is able to swallow oral medications.			
12. The patient has adequate organ function for all of the following criteria:			
12a. Absolute neutrophil count (ANC) $\geq 1.5 \times 10^9/L$			
12b. Platelets $\geq 100 \times 10^9/L$			

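### Inclusion 7 makes a specimen from the last 42 days an entry condition, with archived tissue only as a fallback, yet the protocol states no use for the tissue

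*Combined protocol and SAP*

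**What the plan says.** Section 3.1 requires patients to meet all of its inclusion criteria. Item 7 is one of them: "Be willing to provide tissue from a newly obtained core or excisional biopsy of a tumor lesion". The checklist in Appendix A repeats the item, including the time window: "Newly-obtained is defined as a specimen obtained up to 6 weeks (42 days) prior to initiation of treatment on Day 1". The same item has a fallback: "Subjects for whom newly-obtained samples cannot be provided (e.g. inaccessible or subject safety concern) may submit an archived sample".

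On what might be done with tissue, Section 2.5 says: "See above; no correlative studies will be done in this study". Section 8 says: "No study specific correlative procedures are planned". It adds: "Analysis of exploratory biomarkers will utilize data derived from standard of care testing platforms".

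The schema in the synopsis mentions pre-screening, in which "molecular analysis will be performed to determine if patients have" BRAF V600E-negative disease. It does not name the specimen and does not refer to item 7.

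**The concern.** An invasive entry condition should serve an objective, an endpoint, an eligibility decision or a stored-sample plan, and the protocol should say which. Here it names none.

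Two things are at stake. The first is procedure risk. Section 2.1.1 describes a disease with median survival of 3 to 4 months and significant airway compromise, and Section 2.1.3 notes that patients coming off BRAF-targeted treatment often have to start the next therapy quickly. A biopsy taken only to satisfy item 7 adds a procedure, and possibly delay, without contributing to any result.

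The second is accrual. A patient who declines a feasible biopsy fails an inclusion criterion. Section 12.6.1 puts the lead centre's caseload at fewer than 10 patients a year, and Section 3.6 sets primary completion at 24 months, so an entry barrier with no purpose is hard to justify.

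**Working it through.** **1. Search for a use.** Each place where a use for the tissue could appear:

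| Place | What it says about tissue |
|---|---|
| Sections 1.1 and 1.2, objectives | Response rate, OS, PFS and safety; no tissue endpoint |
| Section 2.5 | Rules out correlative studies |
| Section 3, patient population | Next-generation sequencing is already standard for these patients |
| Section 3.1, item 1 | BRAF status from tissue or blood testing |
| Section 8 | No study-specific procedures; exploratory biomarkers from routine testing |
| Table 9-1, calendar | No biopsy or tissue-collection row |
| Section 10, outcome measures | Imaging response, OS, PFS and adverse events |
| Sections 12.3 to 12.5, analyses | No tissue-based variable |

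The nearest candidate is the pre-screening BRAF result. It does not need item 7, because item 1 accepts blood as well as tissue and the testing is described as routine.

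**2. Who is bound by item 7.** Following its text:

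- Specimen taken within the 42 days, including one taken for clinical reasons: satisfied, no further procedure.
- No such specimen, and the lesion is inaccessible or biopsy is a safety concern: an archived sample may be submitted.
- No such specimen, lesion accessible, no safety concern: a new biopsy, or the criterion is not met.

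Only the third group is affected. Its size cannot be derived, because the documents give neither the share of patients with a recent biopsy nor a refusal rate.

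**3. Effect on the design.** The plan's own figures reproduce and do not depend on item 7. With stage sizes 9 and 8, stopping at 0 of 9 and success at 3 or more of 17 (Section 12.6.2),

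P(reject | p) = Σ (x = 1 to 9) b(x; 9, p) × P[Bin(8, p) ≥ 3 − x].

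- At p = 0.05: 0.0466, against a stated limit of 0.05.
- At p = 0.30: 0.9045, against a stated power of 0.9.
- Probability of stopping early at p = 0.05: 0.95^9 = 0.630; expected size 9 + (1 − 0.630) × 8 = 11.96.

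**4. Scale of an accrual effect, by assumption only.** Suppose 5% to 10% of candidates were lost because of item 7. The enrolment target stays at 17, so the number to approach becomes 17/0.95 = 17.9 to 17/0.90 = 18.9, about 1 to 2 more candidates.

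In time, if the lead centre alone enrolled every patient it saw:

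| Patients per year | No loss | 5% loss | 10% loss |
|---|---|---|---|
| 10 | 17/10 × 12 = 20.4 months | 17/9.5 × 12 = 21.5 | 17/9 × 12 = 22.7 |
| 9 | 17/9 × 12 = 22.7 months | 17/8.55 × 12 = 23.9 | 17/8.1 × 12 = 25.2 |

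The rate of 10 lies just above the stated caseload. Participating sub-sites and regional referral, both foreseen in the protocol, would shorten these times.

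**The case against.** The strongest reply is that this is a gap in documentation, not a burden on patients. The criterion asks for willingness. The 42-day window admits biopsies done for clinical care, and Section 9.1.1 already allows clinically indicated assessments to serve as baseline. The fallback covers inaccessible lesions and safety concerns, which protects the patients with threatened airways, and inclusion 3 adds an airway evaluation. Tissue could also feed the routine sequencing from which Section 8 draws its exploratory biomarkers, and a consent form could state a use. Preferring fresh tissue is a legitimate design choice.

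Much of this stands, and it limits the point. A reader might infer any of the following, which the documents do not support:

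- That every patient must have a new biopsy, or that the trial generates up to 17 of them. The window and the fallback contradict this.
- That 1 or 2 of the 17 patients would be lost. Refusals raise the number approached and leave the enrolment target unchanged, and the refusal rate behind such a figure is an assumption.
- That an excisional biopsy could remove a target lesion and create a false response. The order of biopsy and baseline scan is not specified, but core biopsy is equally acceptable, measurable disease is separately required, and nothing indicates that target lesions would be excised. This is speculation.
- That the tissue has no use at all. The text supports only that none is stated.

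What the reply does not remove is the third group in the working. The fallback depends on a new sample being impossible to provide, and its examples are access and safety. An ordinary reading does not extend it to a patient who could be biopsied but prefers not to be.

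**Conclusion.** The point holds in a limited form. Item 7 can oblige a patient with an accessible lesion and no biopsy in the preceding 42 days to choose between a new procedure and exclusion, while the protocol plans no analysis of the specimen. The number of such patients is unknown and may be small. No objective, endpoint, analysis set, decision rule, error rate or sample size is affected.

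The conclusion rests on two readings: that declining a feasible biopsy is not covered by the fallback, and that routine BRAF testing does not depend on the item 7 specimen. It is more than a drafting gap, because following the text as written can exclude a willing trial candidate or prompt a procedure done only for eligibility. It is worth correcting because the change costs no planned result.

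**What to change.** Delete item 7 from Section 3.1 and from the Appendix A checklist. Alternatively, reword both so that existing diagnostic or archived material is accepted by default and a new biopsy is optional. Because inclusion 1 accepts a cytological diagnosis, the revised wording should say whether cytology material suffices.

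If the sponsor does intend to use the tissue, the protocol should state the purpose, bring Sections 2.5 and 8 into line with it, and add a collection row to Table 9-1.

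The change is to wording, plus the usual amendment approval. The downside is less fresh tissue for later research, none of which is in the present plan.

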10.1.3 Measurement Methods

All measurements should be taken and recorded in metric notation using a ruler or calipers. All baseline evaluations should be performed as closely as possible to the beginning of treatment and never more than 30 days before the beginning of the treatment.

The same method of assessment and the same technique should be used to characterize each identified and reported lesion at baseline and during follow-up. Imaging-based evaluation is preferred to evaluation by clinical examination when both methods have been used to assess the antitumor effect of a treatment.

Conventional CT and MRI. These should be performed with cuts of 10 mm or less in slice thickness contiguously. Spiral CT should be performed using a 5 mm contiguous reconstruction algorithm.

CT scans of the neck, chest, abdomen and pelvis will be performed at baseline and every two cycles according to standard of care. Other imaging of these areas such as PET/MRI will be allowed if CT cannot be performed.

MRI of the brain will be performed at baseline and as clinically indicated. Wherever it can be safely given, radiographic contrast agents should be given for the imaging studies.

Response Criteria

(i)

Evaluation of Target Lesions

Complete Response (CR): Disappearance of all target lesions, determined by two separate observations conducted not less than 4 weeks apart. There can be no appearance of new lesions.

Partial Response (PR): At least a 30% decrease in the sum of the longest diameter (LD) of target

lesions, taking as reference the baseline sum LD. There can be no appearance of new lesions.

Progressive Disease (PD): At least a 20% increase in the sum of the LD of target lesions, taking as reference the smallest sum LD recorded since the treatment started, or the appearance of one or more new lesions.

Stable Disease (SD): Neither sufficient shrinkage to qualify for PR nor sufficient increase to qualify for PD, taking as reference the smallest sum LD since the treatment started.

(ii) Evaluation of Non-Target Lesions

Complete Response (CR): Disappearance of all non-target lesions and normalization of tumor marker level.

Incomplete Response/Stable Disease (SD): Persistence of one or more non-target lesion(s) and/or maintenance of tumor marker level above the normal limits.

Progressive Disease (PD): Appearance of one or more new lesions and/or unequivocal progression of existing non-target lesions

(iii) Evaluation of Best Overall Response

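### Inclusion 9 sets no minimum washout for chemotherapy given after earlier radiotherapy: a minor wording error with a real effect on eligibility

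*Combined protocol and SAP*

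**What the plan says.** Three washout rules stand in Section 3.1.

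- **Criterion 9, chemotherapy.** At least 21 days "between last chemotherapy dose and study treatment start (provided the patient did not receive radiotherapy". Separately, acute effects must have recovered to Grade 1 or lower, with alopecia and Grade 2 neuropathy excepted.
- **Criterion 9, note on targeted drugs.** Patients most recently treated with dabrafenib, trametinib or lenvatinib "require a washout period of 1 week from their last dose".
- **Criterion 10, radiotherapy.** "A washout period of at least 14 days is required between end of radiotherapy and study treatment start".

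Criterion 12 adds limits on blood counts and liver tests. No other inclusion or exclusion criterion sets an interval after chemotherapy. Appendix A, item 9, repeats criterion 9 with the same condition, and the checklist must be completed before registration.

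Section 2.1.3 explains the 1-week rule for dabrafenib and trametinib by contrast: "instead of 3 weeks as is required for cytotoxic chemotherapies". It mentions no radiotherapy exception.

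Section 10.1.3 says that baseline evaluations should be done "as closely as possible to the beginning of treatment and never more than 30 days before the beginning of the treatment".

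**The concern.** The radiotherapy condition has no time limit and no sequence. Read as written, a course completed long ago removes the 21-day rule for chemotherapy given last week. Criterion 10 does not fill the gap, because its clock starts at the end of radiotherapy and not at the last chemotherapy dose.

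Two things are at stake. The primary endpoint is tumour response in one uncontrolled arm, with decisions at 1 response in 9 and 3 in 17 (Sections 12.2 and 12.6.2). Shrinkage from a recent cytotoxic dose would be credited to abemaciclib, and no control group would reveal it. Toxicity is affected in the same way. Section 12.5.2 tabulates events that start or worsen on treatment, and Section 7.3.5 lists neutropenia, anaemia and thrombocytopenia as abemaciclib effects. A late effect of recent chemotherapy on blood counts would be hard to tell apart from these.

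**Working it through.** The plan gives no calculated figure to reproduce. The check is to apply the criteria to each treatment sequence and read off the shortest interval allowed between the last chemotherapy dose and Day 1.

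**Inputs.** 21 days, with its condition, and 7 days for the targeted drugs (criterion 9); 14 days from the end of radiotherapy (criterion 10); baseline imaging at most 30 days before treatment (Section 10.1.3).

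**Shortest interval by sequence.**

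1. *Chemotherapy, never radiotherapy.* The condition is met, so the minimum is 21 days.
2. *Last chemotherapy dose on or before the last day of radiotherapy.* The 21-day rule is off. Radiotherapy must have ended at least 14 days before Day 1 and chemotherapy ended no later than that, so the minimum is 14 days.
3. *Chemotherapy after radiotherapy ended.* The 21-day rule is off. Criterion 10 restricts only the end of radiotherapy. There is no minimum.
4. *Most recent treatment dabrafenib, trametinib or lenvatinib.* The minimum is 7 days.

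**Example of sequence 3, with assumed dates.** Radiotherapy ends on day −60 and the last cytotoxic dose is on day −3. Criterion 10 is met, since 60 ≥ 14. The 21-day rule does not apply because the patient received radiotherapy. If the recovery and laboratory limits are met, an interval of 3 days is allowed.

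The order of the intervals makes little sense. Sections 2.1.3 and 3.1 give the targeted drugs only 1 week, because of their short half-lives, yet they keep a fixed minimum while chemotherapy after radiotherapy has none.

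**Is sequence 3 plausible here?** For neck-limited disease, criterion 2a says: "Patients must have received radiation therapy or surgery to primary tumor and have subsequent evidence of ATC". Section 2.1.1 says: "Patients often suffer from distant metastases even after local therapy is completed". Section 2.1.2 says that doxorubicin "is often combined with radiation or surgery as part of multi-modality therapy". Together these describe a population in which many patients will have had radiotherapy and some will have relapsed elsewhere afterwards. None of them describes chemotherapy after radiotherapy with a last dose close to Day 1. The sequence is plausible, but its frequency is not documented.

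**How far can a baseline scan predate a later last dose?** Longest overlap = 30 days − shortest interval.

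- Sequence 1: 30 − 21 = 9 days
- Sequence 2: 30 − 14 = 16 days
- Sequence 4: 30 − 7 = 23 days
- Sequence 3: 30 − 0 = 30 days

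These are outer limits. The recovery criteria and the instruction to scan close to treatment start will make real overlaps shorter. With a 21-day rule, sequence 3 would fall from 30 days to 9, not to zero.

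**The case against.** The strongest reply is that this is loose drafting and that nobody chose a zero-day washout. The condition was most likely meant to pass chemoradiation patients to criterion 10, and Section 2.1.3 shows that the sponsor believes 3 weeks is the rule. That is probably right about intent, and it is why the point is minor. It does not remove the gap. Section 2.1.3 is background, and staff apply the criterion and checklist, which would pass the patient in the example.

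Second, safeguards remain: recovery to Grade 1 or lower, neutrophil and platelet limits, laboratory tests on Cycle 1 Day 1 or within the preceding 24 hours (Section 9.1.4.7), and a second eligibility review (Section 3.4). They make dosing within a few days of chemotherapy less likely. But they measure toxicity at one moment and not remaining antitumour effect, and none sets a minimum time. The rule in Section 10.1.2 that irradiated lesions are measurable only after documented progression limits carry-over from radiotherapy. It does not address a chemotherapy effect on lesions outside the field.

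Third, the response argument is partly about scan timing. Some overlap is possible under every washout rule in the plan, and the 23 days for targeted drugs is left alone here. This stands. The washout correction reduces the overlap for one group and does not cure the scan window.

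Fourth, Section 2.1.1 reports little sustained benefit from existing treatment, and Section 12.1 considers no treatment effective in this setting. A response carried over from one last dose may therefore be uncommon. This is fair, and the documents give no figure to set against it.

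**Conclusion.** The point holds as a minor wording error with a real effect on eligibility. Chemotherapy after earlier radiotherapy has no minimum interval under criterion 9 or the checklist, contrary to the 3 weeks described in Section 2.1.3. The conclusion about the text is secure. It rests on the literal wording and on the absence of any other criterion with a chemotherapy interval.

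The consequence is much less certain. Recent chemotherapy could confound response and toxicity, but the size of the effect cannot be derived.

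A reader might go further and infer that the trial's false-positive rate exceeds its stated 0.05. The documents do not support that. It would need the number of patients treated in this sequence, the timing of their last doses and scans, and the chance of a carried-over response, and none of these is given. Any error-rate figure would only reflect the values assumed. The Simon design figures themselves are untouched by this point. Nor do the documents support reading the exception as a deliberate choice to allow treatment straight after chemotherapy.

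**What to change.** Replace the washout sentence in criterion 9 and in Appendix A, item 9, with:

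> At least 21 days from the last cytotoxic chemotherapy dose; exception: if the last chemotherapy dose was given on or before the last day of radiotherapy, the 14-day interval of item 10 applies.

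This keeps the probable intent for chemoradiation and closes the gap for chemotherapy given later. Leave the recovery requirement and the 1-week rule for dabrafenib, trametinib and lenvatinib unchanged.

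The cost is one sentence in two places, by amendment. The clinical downside is that a few patients with fast-growing disease who had chemotherapy after radiotherapy may wait up to 3 weeks or be lost to the trial. Section 2.1.1 gives a median survival of 3 to 4 months, so that wait is not trivial. It is the same wait that the plan already imposes on chemotherapy patients who never had radiotherapy.
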